### 3.2.7 Exposure duration

The overall duration of LCM exposure for each subject will be calculated as the date of the last dose of LCM minus the date of the first dose of LCM plus 1 day. Gaps in treatment or days with unknown dosing will not be subtracted from the duration of exposure. The duration of LCM exposure will be summarized, separately, as a continuous parameter (in days) and as a categorical parameter, where categories will be defined using the following cumulative 6-month intervals for the Treatment Period: >0 months, >6 months, >12 months, >18 months, >24 months, >30 months, >36 months, >42 months, and >48 months.

Subject-years of LCM exposure in the study is calculated as the duration of exposure (days) divided by 365.25. Subject-years of LCM exposure will be summarized using the following cumulative 6-month time intervals for the Treatment Period: >0 months, >6 months, >12 months, >18 months, >24 months, >30 months, >36 months, >42 months, and >48 months, where 1 month is defined as 28 days.

### 3.2.8 Modal and maximum daily LCM dose

The modal daily LCM dose (mg/kg/day) is defined as the daily LCM dose the subject received for the longest duration during the Treatment Period in SP848.

The maximum daily LCM dose (mg/kg/day) is defined as the highest total daily dose a subject received during the Treatment Period in SP848.

Maximum daily LCM dose will be summarized as a continuous parameter (in mg/kg/day). Modal daily LCM dose will be summarized as a continuous (in mg/kg/day) and categorical parameter, using the following categories (mg/kg/day) for the Treatment Period: 0.0 to <4.0,  $\geq 4.0$  to <6.0,  $\geq 6.0$  to <8.0,  $\geq 8.0$  to <10.0,  $\geq 10.0$  to <12.0, and  $\geq 12.0$ . This will require that tablet doses in mg/day be converted to mg/kg/day. The following steps will be applied:

1. For days for which a subject received oral solution, the total daily dose in mg/kg/day will be classified into 1 of the above categories on a daily basis.
2. For days for which a subject received tablets, the total daily dose in mg/day will be converted to mg/kg/day by dividing the total daily dose in mg/day by the most recently available body weight; the derived dose in mg/kg/day is then classified into 1 of the above categories on a daily basis.
3. Once all total daily doses are converted to mg/kg/day and classified into 1 of the above categories, the modal daily dose is the dose category which was most frequent.

Should study participants receive both oral solution and an oral tablet on the same day, then the individual tablet dose in mg is converted to mg/kg by dividing by the most recently available body weight, and then the individual dose of oral solution in mg/kg is added to the tablet dose in mg/kg to obtain a total daily dose in mg/kg/day.

The modal and maximum daily dose calculations are based on the number of days a subject was on a given daily dose. Gaps in LCM dosing will be excluded from the determination of modal and maximum daily dose (ie, no imputation for days with missing dosing log information will be performed). If a subject was on two different LCM doses for the same duration of time (ie, a tie when calculating modal daily dose), the modal daily dose will be set to the lower of the doses.

For efficacy analyses related to seizure frequency, modal daily LCM dose will be presented as the most frequent dose during the interval of observation for seizure frequency parameter.

In summary tables and listings, modal daily dose will be presented with the following column headers: <4mg/kg/day to represent doses from 0 to <4.0mg/kg/day, 4mg/kg/day to represent doses 4.0 to <6.0mg/kg/day, 6mg/kg/day to represent doses 6.0 to <8.0mg/kg/day, 8mg/kg/day to represent doses 8.0 to <10.0mg/kg/day, 10mg/kg/day to represent doses 10.0 to <12.0mg/kg/day, and  $\geq 12$  mg/kg/day to represent doses greater than or equal to 12.0mg/kg/day.

### 3.2.9 Age and age at first diagnosis

Age at entry into SP848 will be given in years. For direct enrollers and subjects with a complete date of birth available, age at entry into SP848 will use the SDTM derivation in the analysis dataset. For rollover subjects without a complete date of birth available, age at entry into SP848 will be calculated as:

Age at entry into the previous pediatric study + (number of calendar months between the informed consent dates of the previous pediatric study and SP848)/12.

The age at entry into the previous pediatric study is migrated from the previous pediatric study into the SP848 SDTM.

Missing or partial epilepsy diagnosis date will be derived applying all rules for missing data imputation (see Section 4.2.6) and age at diagnosis will use the following formula, where applicable. The age at first diagnosis will be given in years.

If date of birth is a complete date then age at diagnosis will be calculated as:

$$(\text{Date of first diagnosis of epilepsy} - \text{date of birth}) / 365.25$$

If date of birth is a partial date then age at diagnosis will be calculated as:

$$(\text{Enrollment age in years}) - [(\text{Informed consent date} - \text{Epilepsy diagnosis date}) / 365.25]$$

If this produces a negative value then age at diagnosis will be set to zero.

### 3.2.10 Weight band

Study participants will be classified as belonging to one of the following weight bands based on their weight at time of enrollment into study SP848:

- <30kg
- ≥30 to <50kg
- ≥50kg

### 3.2.11 Body mass index

Body mass index (BMI) will be calculated using the formula:

$$\text{BMI} = \text{weight (kg)} / (\text{height (m)})^2$$

### 3.2.12 Seizure Classification Subgroups

Study participants will be classified as belonging to one of the following seizure classification subgroups based on their seizure classification history for the purpose of disposition, demographic, efficacy, and exposure subgroup analyses:

- POS study participants
  - Study participants from SP0966 who reported only Type I seizures
  - Study participants who reported any Type I seizure
- Generalized seizure study participants
  - Study participants from SP0966 unless they reported only Type I seizures
  - Study participants who reported only Type II seizures
- Unclassified
  - Study participants who reported only Type III seizures

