### 3.2.13 Seizure frequency

Seizure frequency per 28 days (SF) will be based on the number of days (D) for which seizure information was provided:

$$\text{SF} = (\text{Number of seizures in the analysis period}) \times (28/D)$$

If a seizure cluster is reported, it will be assigned to the correct seizure type and the highest recorded daily number of seizures of that seizure type during the 28 days prior to the cluster event will be used as the imputed number of seizures for the day on which the cluster occurred. If no other seizures are recorded for that seizure type for the subject in the 28 days prior to the cluster event, the frequency will be set to 1.

If more than 1 cluster event occurred on the same day for a Type II or Type III seizure, the seizure clusters will be assigned to the correct seizure type and the frequency for each cluster event will be set to the highest recorded daily number of seizures of that seizure type during the 28 days prior to the cluster event. If no other seizures are recorded for that seizure type for the subject in the 28 days prior to the cluster event, the frequency will be set to the number of cluster episodes reported.

If more than 1 cluster event occurred on the same day for a Type I seizure, the seizure clusters will be assigned to the correct seizure type and the overall frequency will be set to the maximum of:

- The highest recorded daily number of seizures of that seizure type during the 28 days prior to the cluster event
- The number of cluster episodes reported on that day

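### The seizure classification subgroups in SAP 3.2.12 are neither exclusive nor exhaustive as written, although each participant is to belong to one of them

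*SAP*

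**What the plan says.** Section 3.2.12 opens with a single-membership rule: "Study participants will be classified as belonging to one of the following seizure classification subgroups based on their seizure classification history". It then gives five membership rules under three subgroups.

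- POS: "Study participants from SP0966 who reported only Type I seizures", or "Study participants who reported any Type I seizure".
- Generalized: "Study participants from SP0966 unless they reported only Type I seizures", or "Study participants who reported only Type II seizures".
- Unclassified: "Study participants who reported only Type III seizures".

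Two rules name SP0966. The other three do not say whether they apply to SP0966 participants, and no precedence is given.

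The subgroups are used for disposition (5.1), demographics (6.1), epilepsy history (6.3), medications (6.4), exposure (8.1), adverse events (8.2), palatability (8.5) and the efficacy summaries (10). Sections 10.1.1 to 10.1.4 give seizure frequency, percent change and responders for participants with POS. Section 10.1.5 gives seizure days for participants with generalized seizures.

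On counting, the numerator of the 28-day frequency in 3.2.13 is "Number of seizures in the analysis period", with no seizure type named. Section 2.3.4.2, the heading of 10.1.2, and Sections 10.1.3 and 10.1.4 all name partial-onset frequency.

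**The concern.** A rule that requires one subgroup should return exactly one for every participant. These rules can return two or none. Two programmers could both follow 3.2.12 and obtain different denominators, or subgroup columns that do not sum to the total.

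The classification also decides who enters four of the five secondary efficacy variables in 2.3.4.2: percent change and the two responder variables (POS), and seizure days (generalized). An SP0966 participant with a mixed history that includes Type I could appear in both sets of outputs. A participant from elsewhere with Types II and III but no Type I could appear in neither.

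A related ambiguity is which seizures are counted. The POS subgroup admits participants who also have Type II or III seizures, so the partial-onset label and the general formula can give different percent changes for the same person.

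**Working it through.** **Classification.** The inputs are the five rules in 3.2.12. There are 2 origins (SP0966 or not) and 7 non-empty combinations of Types I, II and III, so 2 × 7 = 14 profiles. Column A applies the rules literally. Column B reads the three rules that do not mention SP0966 as applying only to participants from elsewhere.

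| Origin | Types reported | A: as written | B: restricted |
|---|---|---|---|
| SP0966 | I | POS | POS |
| SP0966 | II | Generalized | Generalized |
| SP0966 | III | Generalized and unclassified | Generalized |
| SP0966 | I+II | POS and generalized | Generalized |
| SP0966 | I+III | POS and generalized | Generalized |
| SP0966 | II+III | Generalized | Generalized |
| SP0966 | I+II+III | POS and generalized | Generalized |
| Other | I | POS | POS |
| Other | II | Generalized | Generalized |
| Other | III | Unclassified | Unclassified |
| Other | I+II | POS | POS |
| Other | I+III | POS | POS |
| Other | II+III | none | none |
| Other | I+II+III | POS | POS |

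- A: 9 profiles in one subgroup, 4 in two, 1 in none (9 + 4 + 1 = 14).
- B: 13 in one, 0 in two, 1 in none (13 + 0 + 1 = 14).

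The restriction removes every overlap but leaves the gap, which needs its own rule. A participant from outside SP0966 with no recorded type also meets no rule under either reading. These are counts of profiles, not of participants; the SAP gives no participant counts by profile.

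**Counting.** Section 3.2.14 defines percent change as (SF on treatment − SF at Baseline) / SF at Baseline × 100. Take a POS participant not from SP0966 with an assumed 4 Type I seizures per 28 days at Baseline, falling to 1, and k Type II seizures that do not change.

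- Type I only: (1 − 4)/4 = −75%, which meets the ≥75% responder definition.
- All types: −3/(4 + k).
  - k = 0: −75%.
  - k = 2: −3/6 = −50%.
  - k = 12: (13 − 16)/16 = −18.75%, a non-responder on both definitions.

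In this example, any k above 0 loses ≥75% status and any k above 2 loses ≥50% status. The counts are assumed and serve only to show that the choice matters.

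**The case against.** The intended reading can be inferred. The first POS rule would be redundant if the second also covered SP0966, so SP0966 participants are probably meant to follow only the SP0966 rules. Section 6.3.1 supports this, since it allows a Type I history within the generalized group. On that reading no profile falls in two subgroups. This stands as an account of the intent, but 3.2.12 does not say so, and the gap remains either way.

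The gap is narrow. Sections 2.4.1.2 and 2.5 describe direct enrollers (about 100, plus 46 in Japan and 60 in China) largely as having partial-onset seizures. It would arise mainly among rollovers from studies open to epilepsy in general, such as EP0060. Those participants would still be in the overall tables. This also stands.

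A reader might infer that the partial-onset frequency necessarily includes generalized and unclassified seizures. The documents do not support that. The formula in 3.2.13 is general, its cluster rules assign counts to a seizure type, and 2.3.4.2 and 10.1.2 to 10.1.4 use the partial-onset label. However, 10.1.2 expressly limits only the by-type analysis to seizures of that type. The overall POS analysis has no such sentence, and the text of 10.1.1 and the body of 10.1.2 omit the partial-onset qualifier. What remains is an ambiguity between label and formula.

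Finally, all summaries are descriptive, no primary efficacy variable is defined (2.3.4.1), and the overall primary safety results do not depend on the subgroup. That limits the consequence without making the rule workable.

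**Conclusion.** The point holds as a defect of definition. As written, 4 of 14 profiles meet two subgroups and 1 meets none, contrary to the single-membership rule. The overlaps are SP0966 with Type I plus II and/or III (POS and generalized) and SP0966 with Type III only (generalized and unclassified). SP0966 participants with Types II and III only are generalized without conflict.

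A reader might conclude that every SP0966 participant with Types I and II will be counted twice. The text permits this but does not establish it, because a programmer who infers the intent would avoid it.

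The effect is confined to subgroup tables and to the POS-only and generalized-only secondary efficacy outputs. Its size in participants cannot be derived from the SAP. The counting question is a separate request for clarification; its −75% against −18.75% contrast rests on assumed seizure counts.

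**What to change.** In 3.2.12, limit the any-Type-I, only-Type-II and only-Type-III rules to participants not from SP0966. SP0966 participants with only Type I are then POS and all other SP0966 participants are generalized, in line with 6.3.1. Add a line assigning participants from outside SP0966 with Types II and III but no Type I, and a line for participants with no recorded type. Nothing in the SAP decides which subgroup these should join, so the sponsor should choose and state it.

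In 10.1.1 to 10.1.4, state that only Type I seizures are counted, both at Baseline and on treatment.

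The cost is SAP wording and one derivation; no new data are needed.

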### **10.1.3 $\geq 50\%$ reduction in 28-days partial-onset seizure frequency**

For study participants with POS, the number and percentage with  $\geq 50\%$  reduction in 28-day partial-onset seizure frequency ( $\geq 50\%$  responders) will be summarized by seizure time intervals (as defined in Section 3.2.21) and by seizure type (simple partial, complex partial, secondarily generalized). Any subject with seizure data during the time interval will be included in the summary for that seizure time interval and by seizure type.

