### **10.1.5 Seizure days per 28 days (subjects with generalized seizures only)**

For study participants with generalized seizures, the number of seizure days per 28 days (as defined in Section 3.2.16) will be summarized descriptively during the treatment period.

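### The seizure classification bullets in SAP Section 3.2.12 overlap for some SP0966 participants and miss one pattern outside SP0966, so the POS and Generalized denominators are not fixed

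*SAP*

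**What the plan says.** SAP Section 3.2.12 opens with an exclusive rule: "Study participants will be classified as belonging to one of the following seizure classification subgroups based on their seizure classification history". Three subgroups follow.

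- **POS** has two bullets: "Study participants from SP0966 who reported only Type I seizures" and "Study participants who reported any Type I seizure".
- **Generalized** has two bullets: "Study participants from SP0966 unless they reported only Type I seizures" and "Study participants who reported only Type II seizures".
- **Unclassified** has one bullet, for participants whose reported seizures were all Type III.

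The section gives no order of precedence and no residual category.

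Section 10 applies these levels to the efficacy analyses. Section 10.1.2 (percent change) and Section 10.1.3 ("For study participants with POS, the number and percentage with" a reduction of at least 50%) are for POS participants, and Section 10.1.4 repeats 10.1.3 at 75%. Section 10.1.5 covers the other group: "For study participants with generalized seizures, the number of seizure days per 28 days". The same subgroups are used for disposition (5.1), demographics (6.1), epilepsy history (6.3), medications (6.4), exposure (8.1) and adverse events (8.2).

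**The concern.** A rule that puts each participant in one subgroup must give every seizure history exactly one home. Here the bullet on any Type I seizure is not limited to participants from outside SP0966, so it appears to claim SP0966 participants whom the Generalized bullet also claims. Outside SP0966, Generalized requires Type II alone and Unclassified requires Type III alone. A history of both, without Type I, fits neither.

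The subgroup decides which secondary variable a participant contributes to. Two programmers following this text could produce different denominators for the POS responder rates and for seizure days per 28 days. A literal implementation would also give subgroup counts that need not add up to the analysis set. Because the study is open-label, a choice left to programming would be made with outcomes visible.

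**Working it through.** The SAP gives no figure to reproduce here, so the check is an enumeration.

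**Inputs.** Origin is SP0966 or another source (2 levels). Reported seizure types are any non-empty subset of {I, II, III}, which gives 2³ − 1 = 7 sets. That makes 2 × 7 = 14 profiles. The rules are the five bullets of Section 3.2.12.

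**Step 1: the bullets as written.**

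| Types reported | From SP0966 | Not from SP0966 |
|---|---|---|
| I | POS | POS |
| II | Generalized | Generalized |
| III | **Generalized and Unclassified** | Unclassified |
| I + II | **POS and Generalized** | POS |
| I + III | **POS and Generalized** | POS |
| II + III | Generalized | **none** |
| I + II + III | **POS and Generalized** | POS |

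Result: 9 profiles assigned once, 4 twice, 1 never (9 + 4 + 1 = 14).

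**Step 2: the unrestricted POS and Generalized bullets read as applying only outside SP0966, with the Unclassified bullet left literal.** The three POS/Generalized overlaps disappear. SP0966 with Type III only stays in two subgroups, and non-SP0966 with Types II + III stays in none. Result: 12 once, 1 twice, 1 never.

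**Step 3: as Step 2, with the Unclassified bullet also limited to non-SP0966.** Result: 13 once, 0 twice, 1 never. The gap for non-SP0966 Types II + III remains.

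**Step 4: as Step 3, with the non-SP0966 Generalized bullet widened to any Type II without Type I, with or without Type III.** In SP0966, 1 profile is POS and 6 are Generalized. Elsewhere, 4 are POS, 2 Generalized and 1 Unclassified. Result: 1 + 6 + 4 + 2 + 1 = 14, all assigned exactly once.

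**Can the problem profiles occur?** For the overlap, Section 6.3.1 describes how Type I and Type III histories are recorded for generalized participants. Under Section 3.2.12, a Generalized participant can have a Type I history only through the SP0966 bullet, since the other Generalized bullet requires Type II alone. The plan therefore foresees mixed SP0966 histories and expects them in Generalized, while the literal POS bullet claims them too. For the gap, direct enrollers have partial-onset seizures (Section 2.4.1.2), but Section 2.5 describes the up to 100 entrants from EP0060 only as having epilepsy. A Type II plus III history without Type I is therefore not ruled out.

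**Which outputs depend on it?** Section 2.3.4.2 lists five secondary efficacy variables. Four are defined on one of these populations: percent change, 50% responders and 75% responders on POS, and seizure days on Generalized. Seizure-free status is also presented overall, so only its subgroup and POS-by-seizure-type tables are affected.

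**The case against.** The strongest reply is that the intended rule is easy to see. SP0966 has its own bullet under POS and under Generalized, and those two bullets are complementary and cover all of SP0966. If the bullet on any Type I also covered SP0966, the first POS bullet would do no work. Section 6.3.1 supports the same reading. On that view the text lacks only a few words saying that the other bullets are for participants from elsewhere.

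Much of this stands, and the fix below adopts that reading. But the SAP does not contain the limiting words. They must be supplied for the Unclassified bullet as well before every overlap is removed, and the non-SP0966 Type II plus III gap survives regardless. It could be said that Section 10.1.5, taken as ordinary English, covers anyone with Type II seizures. Section 10, however, ties the efficacy subgroups to the Section 3.2.12 levels, where such a person has no place.

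It is also fair to reply that little rides on this. Section 3.1 makes all summaries descriptive, the primary variables in Section 2.3.1 are adverse events and withdrawals, and Section 4.2.5 says that efficacy is not the primary objective. That stands and limits the severity.

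**Conclusion.** The point holds as a defect in a stated rule: 4 of 14 profiles are assigned twice and 1 is never assigned, although the section promises one subgroup each. What is left unfixed is the denominators of the three POS secondary variables, of the Generalized secondary variable and of the subgroup tables. Overall SS and FAS tables do not change, and no error rate is involved. It should be fixed, but it does not threaten the primary results.

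Three stronger readings are tempting, and the document does not support them.

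- **That every mixed SP0966 history is counted twice.** SP0966 with Types II + III falls only in Generalized. The POS/Generalized overlap needs Type I in the mix.
- **That a headcount can be given.** The cohort sizes in Section 2.5 sum to 42 + 100 + 46 + 60 + 100 = 348, which leaves 400 − 348 = 52 for other parent studies. These are caps and approximations, the remainder is not specific to SP0966, and the SAP gives no distribution of seizure types. The number affected cannot be computed.
- **That SP0966 participants with Type III only belong in Unclassified.** The specific SP0966 bullet puts everyone from that study in Generalized unless they reported only Type I. Moving them would override an explicit rule.

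The 9/4/1 count assumes only that each participant reported at least one type.

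**What to change.** Amend Section 3.2.12 in three ways.

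1. Limit the three unrestricted bullets (any Type I, only Type II, only Type III) to participants not from SP0966. SP0966 is then classified by its own two bullets alone: only Type I is POS, and all others are Generalized. This agrees with Section 6.3.1.
2. Change the non-SP0966 Generalized bullet to any Type II and no Type I, with or without Type III.
3. Add a programmed check that the three subgroup counts sum to the SS and to the FAS. This would also expose any participant with no seizure type recorded.

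The cost is a few lines of SAP text and one derived variable. No new data are needed.
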